4.3.5 FAILURE OF ABILITY TO OBTAIN A REFERENCE GLUCOSE SAMPLE

This risk will be minimized through use of two sample sites for Reference Glucose Values. The preferred sample site will be a retrograde hand vein intravenous catheter. If the clinical study staff is unable to obtain a venous draw from the retrograde hand vein catheter for any reason, they will obtain a capillary blood sample from a fingerstick. To be clear, if the retrograde hand vein catheter is no longer available as a sample site, the 24-hour closed loop glucose control study may be completed using fingerstick capillary samples as a source for Reference Glucose Values.

4.3.6 FAILURE OF REFERENCE GLUCOSE ANALYZER

In cases where there is no Reference Glucose Value available for a period exceeding 60 minutes, the risk will be mitigated through termination of the study on that subject. An additional risk of relying on reference glucose analyzers is that they may produce inaccurate independent glucose results. This risk will be minimized through use of the Nova StatStrip Hospital Glucose Meter System, which the FDA has approved for use in the ICU setting.

4.3.7 FAILURE OF CONTROL ALGORITHM TO PERFORM AS EXPECTED

The risk of the control software to not perform as expected has been mitigated through version control of the software. In addition, the rules and sequencing of the software have been independently verified by the both the designer of the software, and the software developer. Furthermore, the control software to be used in this study has been tested in two simulation studies, two animal studies, and a first in human study with no instances of software failure, and excellent overall glucose control capabilities as demonstrated by the previously mentioned results. Finally, the glucose control software has undergone an independent verification and validation process by an outside company (JKI) that specializes in working with the LabVIEW engineering software suite used to create the FUSION systems glucose control software. This verification and validation testing is repeated with each new version of the software, and prior to using the updated software in the clinical setting. The risks of software failure will be mitigated through independent monitoring of the subject's glucose values to prevent the serious risk of hypoglycemia. Complete software failure during the study would lead to termination of the study.

The benefit of using closed loop glucose control software is demonstration of the feasibility of using this software to create a complete glucose control system and outweighs the noted risks.

4.3.8 FAILURE OF SYRINGE PUMPS TO ACCURATELY DELIVER DOSES OF INTRAVENOUS INSULIN AND DEXTROSE

The risk of the syringe pumps to not accurately deliver doses of insulin and dextrose has been mitigated through assessment of their accuracy prior to the study using a balance scale technique.⁸⁹ This testing has demonstrated the accuracy of the syringe pumps to be within $\pm 5\%$ from the prescribed infusion rate/volume. In addition, the infusion pump output rates are monitored by the glucose control software every 10 seconds to ensure the pump output rates match the prescribed rates from the software. If these rate differences are greater than 20%, the study is temporarily stopped until the syringe pump is replaced.

The benefits of using the KDS Legato 100 syringe pumps is that they were designed to work with the LabVIEW software that was used to implement the glucose controller, have a demonstrated infusion rate accuracy of within $\pm 5\%$, and can detect intravenous line occlusion and alert the clinician to this condition (e.g., occlusion) if it is detected.

4.3.9 RISK OF IMPROPER SYRINGE PUMP SET UP

The risk of the study personnel to not properly set up and use the syringe pumps will be mitigated through pre-study tutorials on their use, in addition to making available a standard operating procedure (SOP) as to their original set up and ongoing use. In addition, an IMT representatives will be immediately available for consultation throughout the entirety of the 24 hours of closed loop glucose on each subject.

The benefit of using the KDS Legato 100 syringe pumps is their highly accurate dosing and their compatibility with the LabVIEW software used to develop the FUSION closed loop glucose control system being tested in this study. It is expected that the KDS Legato 100 syringe pumps will not be part of the final FUSION system for which marketing approval will be sought.

4.3.10 RISK OF DIABETIC KETOACIDOSIS (DKA)

DKA is a metabolic condition brought on by lack of sufficient insulin supply such that the body can no longer use glucose as a fuel source, which leads to excessive breakdown of fat, and abnormal labs consisting of elevated blood levels of glucose and beta hydroxybutyrate, with a concomitant lowering of the blood pH. The risk of the participants entering the study while they are in DKA will be mitigated by screening for ketones at the time they are admitted to the CRC on visit 3. This screening will include a capillary blood Reference Glucose Value measured on the Nova StatStrip Hospital Glucose Meter System and blood ketone levels measured on the Nova Max Plus ketone meter (Nova Biomedical).

The risk of the subjects developing DKA while they are in the study will be mitigated by obtaining Reference Glucose Values at least every 1 hour. If the subjects CGM or Reference Glucose Value is > 240 mg/dL, the subjects will have their blood screened for ketones using the Nova Max Plus ketone meter. If the subject's blood ketone level is > 1 mmol/L, they will have venous blood sent for a basic metabolic panel, pH, and beta hydroxybutyrate to determine if they are in DKA. Subjects who are found to be in DKA, during their stay in the CRC during visit 3, will be removed from the study.

The benefit of testing the FUSION system on type 1 and type 2 diabetic subjects, whose blood glucose levels are difficult to control, outweighs the risk of the subjects developing DKA, given the information on the FUSION systems performance that will be gathered during the course of this study.

4.3.11 RISK OF SEVERE HYPERGLYCEMIA

Severe hyperglycemia is defined as a Reference Glucose Value greater than 240 mg/dL. In subjects with type 1 or type 2 diabetes, this degree of hyperglycemia may be a sign that the subject is at risk of developing DKA or hyperosmolar hyperglycemic syndrome (HHS). The risk of subjects developing untreated severe hyperglycemia while they are in the study will be mitigated by monitoring of the subject's Reference Glucose Values at least every 1 hour with the Nova StatStrip Hospital Glucose Meter. CGM alarms will be set up to alert the research nurse and study staff for CGM glucose values > 240 mg/dL for early detection of up trending glucose values. If the subject has a CGM or Reference Glucose Value greater than 240 mg/dL, the risk of DKA will be further mitigated by monitoring the subjects Reference Glucose Values every 30 minutes until their Reference Glucose Value is less than 240 mg/dL. The risk of DKA will be mitigated by terminating the study if a subjects' Reference Glucose Value remains > 240 mg/dL for more than 2 hours.

4.3.12 RISK OF HYPEROSMOLAR HYPERGLYCEMIC SYNDROME

HHS is defined as a serious complication in subjects with type 2 diabetes, and occasionally in subjects with type 1 diabetes, that occurs when the subject experiences severe hyperglycemia (usually >600 mg/dL) for a prolonged period of time. HHS may produce severe dehydration, altered level of consciousness, and coma. The risk of subjects developing HHS while they are in the study is expected to be low and will be mitigated close monitoring of the subject's Reference Glucose Values at least every 1 hour with the Nova StatStrip Hospital Glucose Meter. If the subject has a CGM value greater than 240 mg/dL (detected by CGM alarm set for glucose values > 240 mg/dL) or Reference Glucose Value greater than 240 mg/dL, the risk will be further mitigated by monitoring the subjects Reference Glucose Value every 30 minutes until their Reference Glucose Value is less than 240 mg/dL. Finally, the risk will be mitigated by terminating the study if the subjects CGM or Reference Glucose Value remains > 300 mg/dL for more than 1 hour.

The overall risks of the study are outweighed by the potential benefit of demonstrating the safety of the FUSION systems AI based glucose control software, which is the first step in testing this software with an eventual goal of using it to create a closed loop glucose control system for use in the ICU setting.

5 OBJECTIVES AND ENDPOINTS

DEMONSTRATION OF AN ARTIFICIAL INTELLIGENCE BASED CLOSED LOOP GLUCOSE CONTROL SYSTEM AS A THERAPEUTIC MODALITY IN TYPE 1 AND TYPE 2 DIABETIC PATIENTS

Protocol IMT 2022-1

CONFIDENTIAL

Version1.0.7

22 August 2022

| OBJECTIVES | ENDPOINTS | JUSTIFICATION FOR ENDPOINTS |
|---|---|--|
| Primary | | |
| 
i. Safety
 
To assess the hypothesis that an AI based glucose controller will provide safe glucose control in participants with type 2 diabetes consuming three meals over the course of the 24-hour closed loop glucose control session.
 | 
The percent of all glucose values that are in the hypoglycemic range, when the latter is defined as glucose values less than 70 mg/dL.
 | 
Avoidance of hypoglycemia during tight glucose control leads to decreased mortality rates, and thus measurements of the rate of occurrence of hypoglycemia can be considered an assessment of the overall safety of the glucose control system under study.
 |
| 
2. Efficacy
 
To assess the hypothesis that an AI based glucose controller will provide effective glucose control in participants with type 2 diabetes consuming three meals over the course of the 24-hour closed loop glucose control session.
 | 
The percent of all glucose values that are within the range of 70-180 mg/dL.
 | 
ICU mortality rates increase when patients experience both hypoglycemia (< 70 mg/dL) and hyperglycemia (> 180 mg/dL). Thus, testing the ability of the AI based glucose control system to maintain the study subjects in the range of 70-180 mg/dL will give an indication of its ability to avoid these two deleterious glycemic states.
 |
| Secondary | | |

DEMONSTRATION OF AN ARTIFICIAL INTELLIGENCE BASED CLOSED LOOP GLUCOSE CONTROL SYSTEM AS A THERAPEUTIC MODALITY IN TYPE 1 AND TYPE 2 DIABETIC PATIENTS

Protocol IMT 2022-1

CONFIDENTIAL

Version1.0.7

22 August 2022

| OBJECTIVES | ENDPOINTS | JUSTIFICATION FOR ENDPOINTS |
|--|--|---|
| The secondary objectives of the study are to assess the controller's ability to minimize glucose curve measurements associated with increased ICU morbidity/mortality rates, and to maximize those measurements associated with decreased ICU morbidity/mortality rates. | 
 1. Measure the percent of glucose values that are within the severe hypoglycemic range of 0 – < 54 mg/dL. 2. Measure the percent of glucose values that are within the moderate hypoglycemic range of 54-69 mg/dL. 3. Number of hypoglycemic (< 70 mg/dL) events. Each event separated by at least one glucose value ≥ 70 mg/dL. 4. Measure the percent of all glucose values that are within the desired glucose control range of 100 – 140 mg/dL. 5. Measure the percent of glucose values that are within the range of 70-140 mg/dL. 6. Measure the percent of glucose values that are within the hyperglycemic range of > 140 mg/dL. 7. Measure the percent of glucose values that are within the range of 70-180 mg/dL. 8. Measure the percent of glucose values that are within the hyperglycemic range of > 180 mg/dL. 9. Mean glucose level (mg/dL). 10. Measure of dispersion – coefficient of variation. 11. The study data will be used to determine the percentage of the Dexcom's G6 CGM's glucose values in each zone using a Clarke error grid analysis.¹ This same calculation will be performed on the average of the two Dexcom | The chosen secondary endpoints are routinely measured in glucose control studies and serve to provide a more complete picture of the AI based glucose control systems ability to both safely and effectively provide glucose control. |

DEMONSTRATION OF AN ARTIFICIAL INTELLIGENCE BASED CLOSED LOOP GLUCOSE CONTROL SYSTEM AS A THERAPEUTIC MODALITY IN TYPE 1 AND TYPE 2 DIABETIC PATIENTS

Protocol IMT 2022-1

CONFIDENTIAL

Version1.0.7

22 August 2022

| OBJECTIVES | ENDPOINTS | JUSTIFICATION FOR ENDPOINTS |
|----------------------|---|-----------------------------|
| | G6 CGM systems used by the FUSION system for purposes of glucose control. | |
| Tertiary/Exploratory | | |
| None planned | | |

The glucose data for the above statistical analysis will be the glucose data used by the FUSION system for purposes of glucose control, unless otherwise specified.

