4.3 ASSESSMENT OF POTENTIAL RISKS AND BENEFITS

4.3.1 FAILURE OF DEXCOM G6 CONTINUOUS GLUCOSE MONITOR(S)

The risk of complete failure of the continuous glucose monitoring system will be mitigated through use of two Dexcom G6 CGM systems, which will provide redundancy to this critical component of the FUSION artificial pancreas system. In addition, replacement of the Dexcom CGM system – sensor, transmitter, or receiver – will be allowed if any of these three components of an individual CGM system experiences a failure. To clarify, the FUSION system uses a simple average of the two Dexcom G6 CGM values to decide what steps to take to bring the subject's blood glucose value into the desired control range. In order to be averaged, these two Dexcom G6 CGM values must be time stamped within 5 minutes of each other. The FUSION system will operate for up to four hours with glucose readings from only one Dexcom G6 CGM system, and for up to 20 minutes with no values from either Dexcom G6 CGM

DEMONSTRATION OF AN ARTIFICIAL INTELLIGENCE BASED CLOSED LOOP GLUCOSE CONTROL SYSTEM AS A THERAPEUTIC MODALITY IN TYPE 1 AND TYPE 2 DIABETIC PATIENTS

Protocol IMT 2022-1

CONFIDENTIAL

Version1.0.7

22 August 2022

system. The FUSION system will automatically shut down after four hours if it has only one Dexcom G6 CGM system available for use. The FUSION system will automatically shut down if it has no Dexcom G6 CGM systems available for use for a period of time exceeding 20 minutes.

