The Dexcom G6 CGM Sensor/Transmitter pair communicate via Bluetooth, to the Dexcom G6 Receiver. IMT has not altered in any way, how the Dexcom G6 CGM system works or handles communications between the Transmitter and Receiver. The Dexcom G6 CGM system sends new glucose values to the Receiver every 5 minutes, if they are available, from the Sensor/Transmitter pair attached to the subject. The Dexcom G6 CGM manual notes that the Transmitter and Receiver must be within 20 feet of each other, with no obstacles between them (e.g., walls) in order to effectively communicate via Bluetooth. The FDA is aware of the 20 foot range limitation of the Dexcom G6 CGM system and has approved this CGM system for use in artificial pancreas systems. IMT has developed software called a Driver, that queries the database of the Dexcom G6 Receiver, every 30 seconds, for new glucose values. When the Driver discovers new date/time stamped glucose values in the database of the Receiver, it brings these values into a glucose queue within the FUSION system for use by the FUSION system. The FUSION system will only average glucose values that are time stamped within 5 minutes of each other. The all-in-one Medical Computer running the FUSION systems software is connected to the Dexcom G6 CGM Receiver via a serial data cable. In our internal testing, each Dexcom G6 CGM Receiver was able to receive new glucose values from the Dexcom G6 Transmitter 99.53% of the time within the designed 5 minute time interval.

The benefit of using the Dexcom G6 CGM is that the FDA has already approved this system for use as an integrated continuous glucose monitor (iCGM) in automated insulin dosing (AID) systems for use in treatment of patients with diabetes in the outpatient setting. This study and follow-up studies to be performed in the ICU setting will attempt to demonstrate the feasibility of using the Dexcom G6 CGM system in an AID system (e.g., FUSION) designed for use in the inpatient setting.

In addition, the study will also demonstrate the ability of the Dexcom G6 transmitter to simultaneously transmit its glucose data to one medical device (e.g., the Dexcom G6 Receiver) and the Dexcom G6 Follow App on a mobile phone placed 15 feet from the subject's bed. Demonstration of this functionality is important, as a mobile phone device will be needed in the ICU setting to provide remote monitoring (e.g., outside of the room) of the subject's continuous glucose measurements.

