11.1 STATISTICAL MEASUREMENTS

Primary Safety and Efficacy Endpoints:

1. Safety

The safety of the FUSION system will be determined by its ability to avoid hypoglycemia in adult type 1 and type 2 diabetic patients consuming three meals over a period of 24 hours. Safety will be measured by calculating the percent of all glucose values that are within the hypoglycemic range of less than 70 mg/dL.

Statistics – No statistical comparison will be made for this measurement.

2. Efficacy

The efficacy of the FUSION system will be determined by its ability to maintain glucose in the normal range in adult type 1 and type 2 diabetic patients consuming three meals over a period of 24 hours. Efficacy will be measured by calculating the percent of all glucose values that are within the normal glucose range of 70-180 mg/dL.

Statistics – No statistical comparison will be made for this measurement.

Secondary Efficacy Endpoints:

The secondary objectives of the study are to assess the controller's ability to minimize glucose curve measurements associated with increased ICU morbidity/mortality rates, and to maximize those measurements associated with decreased ICU morbidity/mortality rates.

1. Measure the percent of glucose values that are within the severe hypoglycemic range of 0- <54 mg/dL.

Statistics – No statistical comparison will be made for this measurement.

2. Measure the percent of glucose values that are within the moderate hypoglycemic range of 54-69 mg/dL.

Statistics – No statistical comparison will be made for this measurement.

3. Measure the number of hypoglycemic (< 70 mg/dL) events.

Statistics – No statistical comparison will be made for this measurement.

DEMONSTRATION OF AN ARTIFICIAL INTELLIGENCE BASED CLOSED LOOP GLUCOSE CONTROL SYSTEM AS A THERAPEUTIC MODALITY IN TYPE 1 AND TYPE 2 DIABETIC PATIENTS

Protocol IMT 2022-1

CONFIDENTIAL

Version1.0.7

22 August 2022

4. Measure the percent of all glucose values that are within the desired glucose control range of 100-140 mg/dL.

Statistics – No statistical comparison will be made for this measurement.

5. Measure the percent of glucose values that are within the range of 70-140 mg/dL.

Statistics – No statistical comparison will be made for this measurement.

6. Measure the percent of glucose values that are within the hyperglycemic range of > 140 mg/dL.

Statistics – No statistical comparison will be made for this measurement.

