11.4.3 ANALYSIS OF THE SECONDARY ENDPOINT(S)

For the secondary endpoints that measure percent time in range, the values will be calculated as noted above in 9.4.2. These results will be presented as median and interquartile range (25-75).

The number of hypoglycemic events less than 70 mg/dL will be presented as median and interquartile range (25-75).

The mean glucose level will be presented as mean \pm SD.

The coefficient of variation will be presented as median and interquartile range (25-75).

The Clarke error grid analysis will be presented as a graph of the Clarke error grid. The Reference Glucose Value (Nova StatStrip Hospital Glucose Meter System) and Dexcom G6 data will be analyzed to determine the percent of all values that are in zones A, B, C, D and E.

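### One FUSION value at or above 70 mg/dL ends a hypoglycemic event, so a single low near 70 mg/dL can be counted as several

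*Combined protocol and SAP*

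**What the plan says.** Section 5 (Objectives and Endpoints), secondary endpoint 3, is the number of events below 70 mg/dL, with the separation rule "Each event separated by at least one glucose value" at or above 70 mg/dL. Section 11.1 repeats the endpoint only as "Measure the number of hypoglycemic (< 70 mg/dL) events", and section 11.4.3 adds only that it is summarised by median and interquartile range. None of these places sets a minimum event length, a period of sustained recovery, or a treatment of missing or single-CGM values.

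The series to be counted is fixed at the end of section 5: "The glucose data for the above statistical analysis will be the glucose data used by the FUSION system for purposes of glucose control", unless stated otherwise. Section 4.3.1 explains how that value is formed: "the FUSION system uses a simple average of the two Dexcom G6 CGM values", on data for which "The Dexcom G6 CGM system sends new glucose values to the Receiver every 5 minutes". It also allows one-sensor operation: "The FUSION system will operate for up to four hours with glucose readings from only one Dexcom G6 CGM system". Protocol 2, item 17, raises a discrepancy alarm only when a CGM is more than 20% away from the average.

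**The concern.** The rule has no hysteresis: the threshold that starts an event also ends it, on one value. When true glucose sits a few mg/dL below 70, a small upward error in one 5-minute value ends the event and the next value starts another. The same happens with no change in glucose if the lower-reading sensor drops out and returns.

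This endpoint is the plan's only count of episodes. If it partly counts sensor behaviour, a reader cannot tell a subject with three separate lows from a subject with one shallow low read three times. The error also depends on depth and duration: lows that linger near the threshold are fragmented more than deep, brief ones.

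**Working it through.** The plan states no expected event count and no noise level, so there is no figure of its own to reproduce. I applied its rule directly: a new event starts at each first value below 70 that follows a value at or above 70.

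**1. Sensor switching (inputs from section 4.3.1 and Protocol 2, item 17).** Without an alarm, a CGM may read up to 1.2 times the average. If the lower-reading CGM is lost, the control value can reach 70 or more whenever the average is at least 70 / 1.2 = 58.3 mg/dL.

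- Example: CGMs at 56 and 76. Average = (56 + 76) / 2 = 66; deviation = 10 / 66 = 15.2%, so no alarm.
- Hold this for 60 minutes and drop the lower CGM at two separate readings. The control value becomes 76 twice, and 1 event becomes 3.
- If the higher CGM is lost instead, the value falls to 56 and the count stays at 1.

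How often could this happen? Section 4.3.1 reports 99.53% receipt per receiver. Over 24 hours there are 288 values, so 288 × 0.0047 = 1.35 are missed per CGM. In a 60-minute low (12 values), the chance that the lower CGM misses at least one is 1 − 0.9953^12 = 0.055. This assumes independent misses and that a miss forces single-CGM use. Section 4.3.1 lets values time-stamped within 5 minutes of each other be averaged, so the second assumption is not established.

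**2. Noise near 70.** Design: one true dip, a cosine from 90 mg/dL to a lowest value of 60, 65 or 68 and back over 120 minutes; 5-minute values; AR(1) noise on the control value; 4,000 traces per cell. Assumed noise: SD 2-6 mg/dL, lag-1 (5-minute) autocorrelation 0 or 0.7. Means are over traces with at least one value below 70. Selected cells, including the extremes:

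| Lowest true value | SD | Autocorrelation | Events, plan's rule | Dips split | Events, three values ≥70 to end |
|---|---|---|---|---|---|
| 60 | 2 | 0.7 | 1.00 | 0% | 1.00 |
| 60 | 2 | 0 | 1.07 | 7% | 1.00 |
| 60 | 6 | 0 | 2.23 | 77% | 1.07 |
| 65 | 2 | 0.7 | 1.04 | 4% | 1.00 |
| 65 | 4 | 0.7 | 1.31 | 27% | 1.03 |
| 65 | 6 | 0 | 2.64 | 88% | 1.17 |
| 68 | 2 | 0.7 | 1.14 | 14% | 1.00 |
| 68 | 4 | 0.7 | 1.36 | 32% | 1.04 |
| 68 | 6 | 0 | 2.63 | 90% | 1.29 |

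The true count is 1 in every row. Autocorrelation matters as much as SD: at 0.7 with SD 2-4 the plan's rule gives 1.00 to 1.36.

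**3. Dependence on shape.** A second design put noise on each of two CGMs, averaged them, and set the time below 70 directly. A low to 68 lasting 60 minutes gave 1.68 (SD 2, autocorrelation 0.7) to 3.79 events (SD 3, independent noise). A low to 60 lasting 30 minutes gave 1.00 at SD up to 3 and at most 1.08 at SD 5. The range in step 2 therefore belongs to its dip shape and is not a bound.

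**The case against.** The rule is explicit and set in advance, and it matches the sponsor's swine study (section 3.2, note to Table 7), where an event was a contiguous run ended by a non-hypoglycemic value. Splitting errs against the device, so it is conservative for a safety count. The endpoint is descriptive, with no hypotheses (section 11) and no comparison (section 11.1), in eight subjects; the earlier two-subject study had no time below 70 (section 4.1). Averaging two CGMs and autocorrelated error both reduce splitting, and 15 minutes is a convention that the documents do not require. All of this stands. It limits the importance of the point but does not make one reading a sound marker of recovery.

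Three stronger readings are tempting and are not supported.

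- *Hypoglycemia reporting as a whole is distorted.* The percentages of values below 70, below 54 and from 54 to 69 do not use the separation rule. Nor does the percent of subjects needing rescue medicine (section 11.4.4). The termination criteria in sections 9.1 and 9.2 rest on Reference Glucose Values below 54, not on this count.
- *Any switch between one and two CGMs splits a low.* Only loss of the lower-reading CGM can. With CGMs at 60 and 82 the average is 71, so there is no low to split; losing the higher one gives 60, a false start, and a new end rule would not remove it.
- *The count will be inflated by a known factor.* The documents give no noise figure, and with deep lows and low, correlated noise the effect vanishes.

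**Conclusion.** The point holds as a minor one. Followed exactly, the plan can count one low near 70 mg/dL as several, through noise or through loss of the lower-reading CGM. Under the assumed noise, a single 120-minute dip to 60-68 mg/dL gives 1.00 to about 2.6 events, with 0% to about 90% of dips split. A three-value end rule gives 1.00 to about 1.3. These figures rest on the assumed SD, autocorrelation, dip shape and 5-minute spacing, none of which can be checked against observed data in the documents. By the reported receipt rate, the switching route looks uncommon. The consequence is confined to one untested secondary count, and may not arise at all if few values fall below 70.

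**What to change.** In sections 5 and 11.4.3:

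- Define an event as ended only after at least 15 consecutive minutes in which all available FUSION values are at or above 70 mg/dL, each value being taken to hold until the next. Word this in minutes, not in a number of values, because section 2.3 has the controller adjusting every 5 or 10 minutes.
- Report the single-value count beside it. This keeps comparability with the swine-study definition.
- List each event's duration and lowest value.
- Flag any event that starts or ends at a change between one-CGM and two-CGM values.

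This costs a few sentences and minor programming, and no added data collection beyond keeping the individual CGM values behind each control value. The drawback is that a true recovery shorter than 15 minutes merges with the next low; the paired counts would show it. The end rule does not remove isolated false starts, but the flag identifies those caused by switching. The change is best made before event counts are seen, since a later one would look data-driven.
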